### **3.1.1.2 Rules for Enrollment**

The rules that will be applied for enrolling patients in each group are described below, using the criteria provided in [Section 3.1.1.1](#). Decisions will be made by a safety committee whose composition is described in [Section 8](#).

Sites will enroll and start the dosing of patients in both groups. Once enrollment has reached **5 patients in either group**, enrollment will be paused, the safety data of those 5 patients will be reviewed by the safety committee after all 5 have completed at least one week of dosing, and further enrollment will depend on whether the findings are satisfactory or raise safety concerns.

If the first group to reach an N of 5 is **Group A** (low-dosage):

- If there are no safety concerns after one week of dosing, the safety committee will issue approval for enrollment of all remaining patients in Group A and enrollment in Group B up to 5 patients. (The criteria for enrollment in Group B are described below.)
- If 2 or more of the first 5 patients in Group A reach the criteria defined in [Section 3.1.1.1](#), the committee will issue approval for enrollment of just 5 more patients in Group A, and enrollment in Group B will be put on hold. Dosing of the first 5 Group A patients will continue, and the committee will review the data of the 10 Group A patients once all of them have completed at least 1 week of dosing.
  - At this point, if there are no safety concerns, the committee will issue approval for enrollment of the final 5 patients in Group A and for enrollment of Group B to resume, as per the criteria described for that group.
  - If 4 or more of the 10 patients in Group A who have been dosed to date reach the criteria defined in [Section 3.1.1.1](#), enrollment of additional patients in both groups will be put on hold, and the following processes are to be conducted:
    - Any patients who have reached the criterion and are symptomatic and/or have other associated abnormal laboratory values are to be withdrawn from the study.
    - Patients who did not reach the criterion and for whom there are no other safety concerns should continue dosing.
    - Patients who did reach the criterion but are asymptomatic and do not have any other associated abnormal laboratory values should continue dosing, but must have their enzyme levels monitored every 2 days:

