      - If just one patient experiences a confirmed elevation of ALT and/or  $AST \geq 10 \times ULN$ , that patient is to be withdrawn from the study, but enrollment of the final 5 Group A patients may proceed.
      - If two or more patients experience a confirmed elevation of ALT and/or  $AST \geq 10 \times ULN$ , treatment is to be interrupted for all patients, and the safety committee must promptly meet to review all available safety data and recommend whether or not the study should continue.

If the first group to reach an N of 5 is **Group B** (high-dosage):

- If there are no safety concerns after one week of dosing, enroll all remaining patients in the study.
- If 2 or more of the first 5 patients in Group B reach the criteria defined in [Section 3.1.1.1](#), the committee will issue approval for enrollment of just 5 more patients in Group B. Dosing of the first 5 Group B patients will continue, and the committee will review the data of the 10 patients once all of them have completed at least 1 week of dosing. (Enrollment may continue in the meantime in Group A, provided the stopping criteria defined for that group are not met.)
  - At this point, if there are no safety concerns, the committee will issue approval for enrollment of the final 5 patients in Group B.
  - If 4 or more of the 10 patients in Group B who have been dosed to date reach the criteria defined in [Section 3.1.1.1](#), enrollment of additional patients in Group B will be put on hold, and as the processes described below are to be conducted. (Enrollment may continue in the meantime in Group A, provided the stopping criteria defined for that group are not met.)
    - Any patients who have reached the criterion and are symptomatic and/or have other associated abnormal laboratory values are to be withdrawn from the study.
    - Patients who did not reach the criterion and for whom there are no other safety concerns should continue dosing.
    - Patients who did reach the criterion but are asymptomatic and do not have any other associated abnormal laboratory values should continue dosing but must have their enzyme levels monitored every 2 days:
      - If just one patient experiences a confirmed elevation of ALT and/or  $AST \geq 10 \times ULN$ , that patient is to be withdrawn from the study, but enrollment of the final Group B patients may proceed.

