      - If two or more patients experience a confirmed elevation of ALT and/or  $AST \geq 10 \times ULN$ , treatment is to be interrupted for all patients, and the safety committee must promptly meet to review all available safety data and recommend whether or not the study should continue

Repeat assessments to confirm laboratory results may be performed. The decision on whether to put the study on hold or terminate it will be made by the safety committee.

If a confirmed elevation of ALT and/or AST > **10 x ULN** is experienced by **two subjects in the same dosage group**, a review of the data must immediately take place to decide whether or not the study should continue. The investigator must report any occurrence of this to the sponsor within 24 hours of occurrence, using the sponsor's SAE form.

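### The adverse branch after the first five patients has no upper limit: at 4 or 5 events it still directs five more enrolments, although the 4-of-10 hold count is already met

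*Combined protocol and SAP*

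**What the plan says.** Section 3.1.1.2 pauses enrolment when either group reaches five patients. The committee reviews those five after at least a week of dosing, and "further enrollment will depend on whether the findings are satisfactory or raise safety concerns".

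For Group A there is one adverse branch, entered at two or more events among the five. Then "the committee will issue approval for enrollment of just 5 more patients in Group A, and enrollment in Group B will be put on hold". Those five stay on treatment in the meantime. The second review is timed by the statement that "the committee will review the data of the 10 Group A patients once all of them have completed at least 1 week of dosing". The hold rule applied there begins "If 4 or more of the 10 patients in Group A who have been dosed to date reach the criteria". The hold stops enrolment in both groups and brings three processes:

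- criterion cases with symptoms or other associated laboratory abnormalities are withdrawn;
- criterion cases without these continue, with enzyme checks every 2 days;
- patients who have not met the criterion continue.

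Group B has the same 2-of-5 and 4-of-10 structure: "the committee will issue approval for enrollment of just 5 more patients in Group B". Its hold covers Group B only.

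The hold can be released. If just one patient has a confirmed value at or above 10 x ULN, "that patient is to be withdrawn from the study, but enrollment of the final 5 Group A patients may proceed". The section also says: "The decision on whether to put the study on hold or terminate it will be made by the safety committee". It permits repeat tests to confirm laboratory results.

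**The concern.** The two rules count the same events cumulatively, but the first has no ceiling. After two or three events, patients 6 to 10 help to decide whether enrolment is held. After four or five they cannot, because the hold count has been reached before any of them is dosed. Read as written, the plan then exposes up to five more of a group's 15 patients on the way to a hold that is already settled.

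Three things wait for the ten-patient review: the enrolment hold itself, the fixed 2-day enzyme checks, and the required withdrawal of symptomatic criterion cases below 10 x ULN. That review needs another five patients with a week of dosing each. If the first review falls at Day 7 of the fifth patient, the second falls at that patient's Day 14 at the earliest (7 + 7). It falls at about Day 28 if the new patients start screening only after approval and use the full 14-day window (7 + 14 + 7). Treatment lasts 28 days. Because the hold can be released, an earlier hold would delay the exposure of those patients and might spare it.

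**Working it through.** The plan gives no operating characteristics for these rules, and section 9.2 states that no formal power calculation can be performed. There is therefore no figure to reproduce.

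**Inputs.** Branch entry at x1 ≥ 2 of 5 and hold at x1 + x2 ≥ 4 of 10 (3.1.1.2, both groups). An event is reaching a value (3.1.1.1), so a standing event is not undone by a later fall. Withdrawn patients are not replaced (4.5.3) and remain among those dosed. The only documented rate near the criterion is about 20% at about 5 x ULN, in healthy volunteers at 100 mg/kg/day (1.1). The true rate p is assumed, as are independence and a common rate.

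**Step 1: can patients 6 to 10 affect the hold?** Counting only new events in those five, P(hold | x1) = P(Y ≥ 4 − x1), with Y ~ Binomial(5, p).

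| Events in first 5 | Needed from patients 6–10 | p = 10% | p = 20% |
|---|---|---|---|
| 2 | 2 or more | 8.1% | 26.3% |
| 3 | 1 or more | 41.0% | 67.2% |
| 4 or 5 | none | 100% | 100% |

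For example, at p = 20%: after 2 events, 1 − 0.8^5 − 5(0.2)(0.8^4) = 1 − 0.32768 − 0.40960 = 0.2627; after 3 events, 1 − 0.32768 = 0.6723. The rows for 2 and 3 are minimum values, because the first five keep dosing and may add events. The last row holds at any p.

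**Step 2: how often does the case arise?** P(X ≥ 4 of 5) = 5p^4(1 − p) + p^5.

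| p | Calculation | Chance |
|---|---|---|
| 10% | 0.00045 + 0.00001 | 0.05% |
| 20% | 0.00640 + 0.00032 | 0.7% |
| 30% | 0.02835 + 0.00243 | 3.1% |
| 40% | 0.07680 + 0.01024 | 8.7% |
| 50% | 0.15625 + 0.03125 | 18.8% |

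Here p is the rate by the time of the five-patient review.

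**Step 3: strength of the two signals.** Clopper-Pearson 95% lower limits are 12.2% for 4/10, which triggers the hold, and 28.4% for 4/5 and 47.8% for 5/5, which do not. Section 9.4.1.3 plans this interval for reporting incidence, not for enrolment decisions; it serves here only as a yardstick. By that yardstick the stronger early signal draws the weaker written response.

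**The case against.** The best counter-argument is that the committee is not bound to enrol. Section 3.1.1.2 gives it the decisions and makes further enrolment depend on the findings. Sections 3.1 and 8 say the same in general terms, and section 14 lets the sponsor stop at any time. This stands as a softening: a careful committee would probably pause at 4 or 5 of 5. However, none of these provisions names a count, and all sit beside a specific directive to approve five more. The separate immediate review needs two confirmed values above 10 x ULN in one group, whereas a patient with a normal baseline meets the criterion at 5 x ULN.

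A reader might infer that patients who meet the criterion are left without required care until the second review. The documents do not support that. Criterion cases must be reported to the sponsor within 24 hours (3.1.1.1, 7.1.1.8.1) and must be followed to resolution, beyond Day 28 if needed (Synopsis, 7.1.2). The individual rules at 10 x ULN apply throughout (3.1.1.1, 4.5.1.1). Investigators may also test more often (7.1.2) or withdraw a patient at their discretion (4.5).

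Two further points stand. The 2-day checks and group-triggered withdrawals are equally absent after two or three events, so only the predetermined hold is specific to this case. And a repeat test could overturn a value, so the hold is certain only if the counts stand.

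**Conclusion.** The point holds as a narrow gap in the group-level rule, in both groups. At a standing 4 or 5 of 5, the written instruction enrols patients 6 to 10 although they cannot alter the hold. It is worth correcting but is not a major flaw.

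A reader might take the higher percentages in the working as a forecast. They are not. At the only documented anchor, 20%, the case has a 0.7% chance. That anchor comes from volunteers dosed without titration (3.3), while patients here are on a stable Ferriprox regimen. The rate in patients is unknown, and the 30% to 50% rows are assumptions. The case does become more likely as the true rate rises, which is when the rule is most needed.

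The exposure at issue is up to five of 15 patients in a group, delayed or possibly spared. The conclusion rests on events standing after any repeat test. The probabilities also rest on independence and a common rate; the certainty of the hold does not.

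**What to change.** In 3.1.1.2, for both groups:

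1. Restrict the branch that allows five more patients to two or three events among the first five.
2. At four or five events, apply that group's existing enrolment hold and its processes at the five-patient review. Allow no further enrolment in the held group or groups unless the safety committee makes an explicit decision to release the hold. Say that this also covers the situation where no patient is confirmed at or above 10 x ULN, since the present release text deals only with one, or with two or more. The decision should name the groups it covers, because the Group A hold applies to both groups while its release line mentions only Group A.
3. If the hold is released, enrol only five more patients in that group, and keep the committee review of all ten after at least a week of dosing before the final five.

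Step 3 matters. A release that opened all remaining places would let ten patients enter with no written review at ten. The count at ten would still be at least four, so that review would again be a hold review. The difference is that patients 6 to 10 would have entered by deliberate decision, with the hold processes already running.

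The thresholds of two and four and all other paths stay as they are. No new data are needed, because the five-patient review already has the counts. The cost is that in this rare case the first hold decision rests on five patients rather than ten, and enrolment may be slower.

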#### **3.1.1.1 Criteria for Safety Concerns**

As a consequence of liver iron overload and frequent blood transfusions, patients in the target population may have fluctuations of AST and/or ALT that frequently exceed the reference ranges. In recognition of this variability, for each of these enzymes, the criteria for deciding whether an individual patient's increases during the current study is of concern will be set as follows:

- For a patient whose baseline level is within the normal range, the criterion will be reaching a value of 5 times the ULN during the study.
- For a patient whose baseline level is above the ULN, the criterion will be reaching a value of 5 times the baseline value during the study or 10 x ULN.

All cases of patients meeting either of the above criteria at any point during the study must be reported to ApoPharma by the investigator within 24 hours of occurrence, using the sponsor's SAE form.

If at any time during the study a patient's ALT and/or AST values reach a level of **10 x ULN**, do the following:

- If the patient is symptomatic and/or has any other clinically significant abnormal laboratory results, immediately withdraw the patient from the study.
- If the patient is asymptomatic and has no other clinically significant abnormal laboratory results, interrupt treatment and obtain a confirmatory count the next day.
  - If the value is confirmed to be  $\geq 10$  x ULN:
    - Stop treatment, withdraw the patient and complete all end of study assessments scheduled for Day 28
    - Document the event and report it within 24 hours to ApoPharma
    - Monitor the patient daily until the elevated value returns to a level that is regarded as not clinically significant
  - If the confirmatory value is found to be  $< 10$  x ULN, resume treatment as per protocol, and monitor liver enzyme levels within 3 days of resuming therapy.

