#### **4.5 Patient Withdrawal**

Patients have the right to withdraw from the study at any time and for any reason without consequence to future care by the investigator or study center.

A patient may be withdrawn from the study at any time, at the discretion of the investigator, for any of the following reasons:

- Medical or safety reasons considered significant by the patient and/or the investigator
- Requirement for concomitant medication that might interfere with the evaluation of study treatment or may be contraindicated
- Receipt of a rescue medication
- Occurrence of other illnesses that might affect the patient's further participation in the study or evaluation of study treatment
- A protocol deviation that might interfere with study assessments, as judged by the investigator
- Repetitive patient non-compliance with the protocol or with instructions of the investigator
- Participation in another clinical trial at any time during the conduct of this study
- Any other situation where, in the opinion of the investigator, continuation of the study would not be in the best interest of the patient

A patient **must** be withdrawn from the study if any of the following conditions apply:

- Pregnant or planning to become pregnant (see [Section 7.1.4](#))
- A confirmed ALT or AST value  $>10 \times \text{ULN}$  (see [Sections 4.5.1.1](#) and [7.1.1.8.1](#))
- A confirmed ANC value  $< 0.5 \times 10^9$  (see [Sections 4.5.1.2](#) and [7.1.1.8.2](#))
- Occurrence of any adverse event characterized as life-threatening or disabling that is not associated with the patient's condition
- Termination of the study by the sponsor

Patients who decide to withdraw participation in the study should always be contacted, if possible, in order to ask about the reason for withdrawal, whether any adverse events (AEs) occurred, and use of concomitant medications. A withdrawn patient should return for an early termination visit and a follow-up visit. All investigational product and materials should be returned. If any AEs occurred, the investigator must attempt to follow up the outcome until resolution.

If a patient withdraws or is withdrawn before completing the study, the date and reason for the withdrawal must be entered on the source document and on the appropriate page of the electronic case report form (eCRF), and all other appropriate eCRF pages must be completed.

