##### **4.5.1.1 Elevated Liver Enzymes**

A patient who reaches an ALT and/or AST value  $\geq 10 \times \text{ULN}$  at any time during the study is to be **immediately** withdrawn if he or she is additionally symptomatic and/or has any other clinically significant abnormal laboratory results. If there are no other signs of concern, a confirmatory count is to be obtained the next day. If the value is confirmed, the patient is to be withdrawn; if it is not, the patient is to be closely monitored. Details are provided in [Section 3.1.1.1](#).

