#### **6.1.1 Dosage Form and Mode of Administration**

Deferiprone DR tablets are to be taken twice a day, approximately 12 hours apart. The route of administration is oral. All patients will take approximately the same total daily dosage that they were taking three times a day with Ferriprox IR, whether that dosage was closer to 75 mg/kg/day (Group A) or closer to 100 mg/kg/day (Group B). The dosage for each subject will be rounded to the nearest multiple of 500 mg. The tablets are scored in a way that they can be split into two halves that maintain the release characteristics of the whole tablets.

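### The hold rules and the individual rule give different dosing instructions for an unconfirmed ALT or AST value at 10 x ULN, and the primary endpoint in Section 9.1.1 does not match the safety criterion it restates

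*Combined protocol and SAP*

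**What the plan says.** **Individual rule.** Section 3.1.1.1 sets the criterion for each enzyme. With a normal baseline it is reaching 5 x ULN. With a baseline above ULN it is reaching 5 times baseline, or 10 x ULN. For a patient whose value reaches 10 x ULN at any time in the study, who has no symptoms and no other clinically significant laboratory abnormality, the instruction is to "interrupt treatment and obtain a confirmatory count the next day". A value confirmed at or above 10 x ULN leads to withdrawal.

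**Hold rule.** Section 3.1.1.2 applies when 2 or more of the first 5 patients in a group, and then 4 or more of 10, have met the criterion. For Group A: "Patients who did reach the criterion but are asymptomatic and do not have any other associated abnormal laboratory values should continue dosing", with enzyme checks every 2 days. The Group B text matches: such patients "should continue dosing but must have their enzyme levels monitored every 2 days". The sub-bullets then act only on a confirmed value at or above 10 x ULN.

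**Withdrawal.** Section 4.5 makes withdrawal mandatory for "A confirmed ALT or AST value" above 10 x ULN and cites Section 4.5.1.1, which uses at or above 10 x ULN and sends the reader to Section 3.1.1.1 for details.

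**Primary endpoint.** Section 2.1 names Section 9.1.1 as the place where the primary endpoint is given. Section 9.1.1 restates the criterion but names ALT twice with no AST, and words the upper limb as above 10 x ULN. The Synopsis (Criteria for evaluation) and Section 3.1.1.1 name both enzymes and speak of reaching 10 x ULN. Section 9.4.1.3 also names both enzymes.

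**The concern.** During a hold, a site with an asymptomatic patient at a first, unconfirmed value of 10 x ULN has two written dosing instructions. One stops treatment pending a next-day retest; the other continues treatment with the next check within 2 days. This is a multi-center study and the first use of the formulation in iron-overloaded patients, so sites could act differently on the same finding.

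The endpoint question is separate. The safety committee counts patients by the criterion in Section 3.1.1.1, while the primary analysis is defined by Section 9.1.1. If the two definitions differ, the count that governs enrollment and the count that is reported need not agree.

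**Working it through.** The plan has no figure to reproduce here: Section 9.2 states that no formal power calculation can be performed. The check is a comparison of texts with some supporting arithmetic.

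**Inputs.** Criterion: Section 3.1.1.1. Highest eligible value at screening, which serves as baseline: 5 x ULN (Section 4.3, exclusion 2; Section 3.1). Hold trigger: Section 3.1.1.2. Dosing frequency: "Deferiprone DR tablets are to be taken twice a day, approximately 12 hours apart" (Section 6.1.1). Group size: 15 (Section 4.1).

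**Step 1: do the two rules cover the same patient?** Let b be baseline as a multiple of ULN, and read the criterion's two limbs as whichever is met first. The threshold is 5 for b ≤ 1 and min(5b, 10) for 1 < b ≤ 5.

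| b | 5b | Criterion first met at (x ULN) | Is a value of exactly 10 counted if 9.1.1 requires above 10? |
|---|---|---|---|
| 0.8 | 4 | 5 | yes |
| 1.5 | 7.5 | 7.5 | yes |
| 2 | 10 | 10 | yes |
| 3 | 15 | 10 | no |
| 5 | 25 | 10 | no |

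Every eligible patient at 10 x ULN has met the criterion as Section 3.1.1.1 states it, so the hold rule covers that patient too. For b from 2 to 5, meeting the criterion means being at the level where Section 3.1.1.1 interrupts treatment.

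**Step 2: the instructions side by side** (asymptomatic, no other abnormality, first value at 10 x ULN, hold in force).
- Section 3.1.1.1: interrupt and retest the next day; 0 doses before the retest.
- Section 3.1.1.2: continue and check every 2 days; up to 2 doses a day x 2 days = 4 doses before the next check.
- Once a value at or above 10 x ULN is confirmed, both sections lead to withdrawal.

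**Step 3: how often could a hold occur?** The documents give no criterion rate for patients on this formulation, so the rate p is an assumption. Take X1 and X2, the counts in two blocks of 5, as independent binomial(5, p), with each patient's status fixed at the block's review and fewer than 2 in the first block releasing enrollment.

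P(hold) = P(X1 = 2)·P(X2 ≥ 2) + P(X1 = 3)·P(X2 ≥ 1) + P(X1 ≥ 4)

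- p = 0.10: 0.0729 x 0.0815 + 0.0081 x 0.4095 + 0.0005 = 0.0097, or 1.0%
- p = 0.20: 0.2048 x 0.2627 + 0.0512 x 0.6723 + 0.0067 = 0.0949, or 9.5%
- p = 0.30: 0.3087 x 0.4718 + 0.1323 x 0.8319 + 0.0308 = 0.2865, or 28.6%

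These are per group. Under the same assumptions they are upper bounds for the conflict, which also needs a patient at an unconfirmed 10 x ULN.

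**Step 4: the operator in Section 9.1.1.** From the last column of the table, a peak of exactly 10 x ULN is counted under either wording when b ≤ 2. For 2 < b ≤ 5 it is counted under reaching 10 x ULN and not under above 10 x ULN. No other value is affected.

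**Step 5: the enzyme slip.** Read literally, AST-only cases drop out. One patient moves a group's incidence by 1/15 = 6.7 points. The Clopper-Pearson 95% interval is 0 to 21.8% for 0/15 and 0.2 to 31.9% for 1/15. The documents give no AST-only rate.

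**The case against.** The best answer to the dosing conflict is structural. Section 3.1.1.1 applies at any time, has no exception for a hold, and is specific to 10 x ULN. The hold text is a general rule for anyone who met the criterion, and it acts on confirmed elevations, which presupposes the confirmation procedure of Section 3.1.1.1. Section 4.5.1.1 also sends the reader to 3.1.1.1, not 3.1.1.2. This stands as the more natural reading of the text, and the figure of 4 doses arises only at a site that follows the hold text literally. But the hold text exempts only confirmed values, and no sentence gives either rule precedence.

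A reader might infer further conflicts that the documents do not support:
- Section 4.5.1.1 says "If there are no other signs of concern, a confirmatory count is to be obtained the next day" without mentioning interruption. It is a summary that defers to Section 3.1.1.1, not a third instruction.
- The sentence "Repeat assessments to confirm laboratory results may be performed" is a general permission for any laboratory result. It does not make the specific next-day retest optional.
- The closing rule of Section 3.1.1.2, which opens "If a confirmed elevation of ALT and/or AST >" 10 x ULN, is a separate rule: two subjects in the same dosage group, leading to a data review. It is not the hold rule with a different operator.
- Sections 4.5 and 4.5.1.1 can both be followed. Every value above 10 is also at or above 10, and Section 4.5 does not say that its list is exclusive.
- Hold outcomes that the rules do not spell out are decisions for the safety committee.

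On the endpoint, naming ALT twice is not a coherent ALT-only definition, and every parallel passage includes AST. An intended exclusion of AST is not a credible reading. The Section 1.2 figures (of 889 patients, 4 stopped for ALT, 1 for both enzymes, none for AST alone) count discontinuations, not criterion events, so they do not size the effect.

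**Conclusion.** The point holds in a narrow form, as an internal inconsistency.

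- **Dosing instruction.** This carries most of the weight. The two sections differ for the same patient state, but only before confirmation and only during a hold. The 1.0% to 28.6% range for a hold rests on assumed criterion rates of 10% to 30% and independence between patients. The only nearby figure, approximately 20% of healthy volunteers dosed at 100 mg/kg/day reaching approximately 5 x ULN (Section 1.1), is from another population, and Section 1.2 hypothesises a less prominent effect in patients. The upper end should not be read as a forecast.
- **Primary endpoint.** Section 9.1.1 does not match the criterion. The operator matters only for baseline above 2 and up to 5 x ULN with a peak of exactly 10 x ULN. The enzyme slip is evidently typographical, but it stands in the governing definition.
- **Withdrawal boundary.** The mismatch between Sections 4.5 and 4.5.1.1 is a lesser point of consistency, limited to a confirmed value of exactly 10 x ULN.

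It would go too far to say that the plan leaves confirmed elevations without a clear rule, or that it drops AST from its primary analysis.

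**What to change.** 1. The sponsor's clinical team should reconcile Sections 3.1.1.1, 3.1.1.2, 4.5 and 4.5.1.1 so that one instruction and one boundary apply to an unconfirmed value at 10 x ULN, including during a hold. Section 3.1.1.2 should cross-refer to Section 3.1.1.1 in both the Group A and the Group B text. This review takes no view on which clinical rule or boundary is right.
2. In Section 9.1.1, replace the second ALT with AST, and make the 10 x ULN wording identical to the criterion in Section 3.1.1.1 as reconciled, so that the committee's count and the primary endpoint share one definition.
3. Use the same operator in Section 4.5 as in Section 4.5.1.1, which it cites.

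The cost is protocol wording only, with no extra patients, visits or assays.
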